3 INVESTIGATIONAL PLAN

3.1 Study Design

This is a multicenter, open-label, single-arm study in subjects with platinum-pretreated, recurrent/metastatic EBV+ NPC (also referred to as NPC in this protocol). The study will be conducted in 2 parts: Cohort 1 will be enrolled as the phase 1B portion to determine the phase 2 dose; Cohort 2 will be enrolled as the phase 2 portion to examine the clinical benefits of combined T cell and checkpoint inhibitor immunotherapies for the treatment of subjects with NPC. The study will enroll 48 to 60 subjects in total. Phase 1B (Cohort 1) will enroll 12 to 24 subjects. For each dose level explored in Cohort 1, at least 6 subjects must have had disease that is refractory to PD-1 or PD-L1 monoclonal antibody. All other subjects enrolled to Cohort 1 will be checkpoint inhibitor naïve subjects (have never received pembrolizumab or other anti-PD-1, anti-PD-L1, anti-PD-L2, anti-CD137, anti-OX40 [CD134] or anti-CTLA-4 products). Dose de-escalation is permitted in Cohort 1 only. Cohort 2 will enroll 36 subjects who are checkpoint inhibitor naïve.

Tabelecleucel will be selected for each subject from the bank of available tabelecleucel cell products based on matching ≥ 2 HLA alleles, at least one of which is a restricting HLA allele, ie, shared between the tabelecleucel source material (donor) and the subject.

The overall treatment schema is shown in [Figure 1](#) and the planned dose cohorts are provided in [Table 2](#). In Cohort 1, tabelecleucel will be administered initially to 12 subjects at a dose of 2×10^6 cells/kg IV on Day 1, Day 8, and Day 15 of a 21-day cycle. Pembrolizumab will be administered to adult subjects (≥ 18 years of age) at a dose of 200 mg IV Q3W (ie, on Day 1 of each 21-day cycle) and to pediatric (adolescent) subjects (12 to < 18 years of age) at a dose of 2 mg/kg IV Q3W. If ≥ 2 of the initial 6, or ≥ 4 of the initial 12, Cohort 1 subjects experience a DLT in the first 21 days, the dose of tabelecleucel will be reduced to 1×10^6 cells/kg/dose, and an additional 12 subjects will be treated with the combination of tabelecleucel at 1×10^6 cells/kg/dose and pembrolizumab at the recommended dose level ([Table 3](#)). Otherwise,

all 12 subjects in Cohort 1 will receive tabelecleucel at 2×10^6 cells/kg/dose and pembrolizumab at the recommended dose level.

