3.4 Safety Data Review Committee

A SDRC composed of representatives from the sponsor and the principal investigators or designated sub-investigators from all sites enrolling subjects in Cohort 1 will review reported DLTs and cumulative safety data to determine further enrollment. The data review will occur as soon as possible after Cycle 1 Day 21 of the last subject in Cohort 1.

The sponsor's medical monitor and global safety officer will review data on an ongoing basis and may suspend dosing and/or enrollment and convene a SDRC meeting at any time based on emerging safety data.

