Note: Dosing interruptions are permitted in the case of medical/surgical events or logistical reasons (ie, elective surgery, unrelated medical events, subject vacation, holidays) not related to the administration of investigation product. Subjects should be placed back on the treatment schedule within 3 weeks of the scheduled interruption, unless otherwise discussed with the sponsor's medical monitor. The reason for dose interruption should be documented in the subject's study record.

5.2.2 *Duration of Treatment and Subject Participation*

The duration of treatment is dependent on a subject's response to treatment and is estimated to be approximately 2 years for subjects with a response to treatment (CR, PR, or SD): a maximum of 4 treatment/consolidation cycles (21-day cycles of 3 infusions of tabelecleucel and 1 of pembrolizumab) and maintenance cycles (84-day cycles of 4 infusions of pembrolizumab and

1 of tabelecleucel) until up to a total of 35 pembrolizumab infusions (including for treatment, consolidation, and maintenance) have been given.

After treatment/consolidation and maintenance cycles, subjects will have an End-of-Treatment visit (30 days after the last dose of investigational product) and then enter Quarterly Follow-up for 12 months after the last dose of investigational product. Before receiving any treatment, subjects must undergo a tabelecleucel inventory check and screening, with screening up to 28 days prior to the first dose of investigational product.

5.2.3 *Definition of Dose-limiting Toxicity*

All toxicities will be graded based on the investigator's assessment using CTCAE version 5, except for certain events described in Section 8.3, which have a separate grading system.

The DLT window of observation will be during Treatment Cycle 1 only (ie, during the first 21-day cycle; adverse events (AEs) meeting the definition of a DLT but occurring after this period will not be considered DLTs).

The occurrence of any of the following toxicities during Treatment Cycle 1 will be considered a DLT, if assessed by the investigator to be possibly related or related to investigational product administration (either tabelecleucel and/or pembrolizumab), excluding toxicities clearly not related to the investigational product, such as disease progression, environmental factors, unrelated trauma, etc.:

- Grade 4 nonhematologic toxicity (not laboratory).
- Grade 4 hematologic toxicity lasting ≥ 7 days, except thrombocytopenia:

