 - Grade 4 thrombocytopenia of any duration
 - Grade 3 thrombocytopenia associated with bleeding that requires a platelet transfusion
- Any nonhematologic AE grade ≥ 3 in severity should be considered a DLT, with the following exceptions: grade 3 fatigue lasting ≤ 3 days; grade 3 diarrhea, nausea, or vomiting without use of anti-emetics or anti-diarrheals per standard of care; grade 3 rash without use of corticosteroids or anti-inflammatory agents per standard of care.
- Any grade 3 or grade 4 non-hematologic laboratory value if:
 - Clinically significant medical intervention is required to treat the subject, or
 - The abnormality leads to hospitalization, or
 - The abnormality persists for > 1 week.
 - The abnormality results in a Drug-induced Liver Injury (DILI)
 - Exceptions: Clinically nonsignificant, treatable, or reversible laboratory abnormalities including liver function tests, uric acid, etc.

- Febrile neutropenia grade 3 or grade 4:
 - Grade 3 is defined as ANC < 1000/mm³ with a single temperature of > 38.3 degrees C (101 degrees F) or a sustained temperature of ≥ 38 degrees C (100.4 degrees F) for more than 1 hour
 - Grade 4 is defined as ANC < 1000/mm³ with a single temperature of > 38.3 degrees C (101 degrees F) or a sustained temperature of ≥ 38 degrees C (100.4 degrees F) for more than 1 hour, with life-threatening consequences and urgent intervention indicated.
- Prolonged delay (> 2 weeks) in initiating Cycle 2 due to treatment-related toxicity.
- Any treatment-related toxicity that causes the subject to discontinue treatment during Cycle 1.
- Missing > 25% of pembrolizumab or tabelecleucel doses as a result of investigational product-related AE(s) during the first cycle.
- Grade 5 toxicity.

Any subject experiencing any DLT will be withdrawn from treatment (both investigational products). Whenever possible, protocol-defined follow-up will be continued after the subject has discontinued investigational product treatment (refer to Section 6.7).

MTD definition: The MTD is defined as the highest dose level at which the subject incidence of a DLTs during the first 21-day cycle of investigational product dosing is < 33%.

RP2D definition: The RP2D is no higher than the MTD and is based on optimal benefit-risk, as determined by the SDRC.

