Myocarditis	Grade 1 or 2	Withhold	Based on severity of AE administer corticosteroids	Ensure adequate evaluation to confirm etiology and/or exclude other causes
	Grade 3 or 4	Permanently discontinue		
All other irAEs	Intolerable/ persistent Grade 2	Withhold	Based on type and severity of AE administer corticosteroids	Ensure adequate evaluation to confirm etiology and/or exclude other causes
	Grade 3	Withhold or discontinue based on the type of event. Events that require discontinuation include and not limited to: Guillain-Barre Syndrome, encephalitis		
	Grade 4 or recurrent Grade 3	Permanently discontinue		

irAEs	Toxicity grade or conditions	Action taken to pembrolizumab ^a	irAE management with corticosteroid and/or other therapies	Monitor and follow-up
Abbreviations: AE: adverse event; ALT: alanine aminotransferase; AST: aspartate aminotransferase; irAE: immune-related AE; IV: intravenous(ly); T1DM: type 1 diabetes mellitus; TBIL: total bilirubin.				
NOTE: For subjects with Grade 3 or Grade 4 immune-related endocrinopathy where withhold of pembrolizumab is required, pembrolizumab may be resumed when AE resolves to grade ≤ 2 and is controlled with hormonal replacement therapy or achieved metabolic control (in case of T1DM).				
^a Withhold or permanently discontinue pembrolizumab is at the discretion of the investigator or treating physician.				

5.2.5.2 *Dose modification and Toxicity Management of Infusion Reactions Related to Pembrolizumab*

Pembrolizumab may cause severe or life-threatening infusion reactions including severe hypersensitivity or anaphylaxis. Signs and symptoms usually develop during or shortly after drug infusion and generally resolve completely within 24 hours of completion of infusion. Dose modification and toxicity management guidelines on pembrolizumab associated infusion reactions are provided in [Table 6](#).

Table 6 Pembrolizumab Infusion Reactions Dose modification and Treatment Guidelines

CTCAE Grade	Treatment	Premedication at Subsequent Dosing
Grade 1 Mild reaction; infusion interruption not indicated; intervention not indicated	Increase monitoring of vital signs as medically indicated until the subject is deemed medically stable in the opinion of the investigator.	None

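### A Cycle 2 delay of more than 2 weeks counts as a DLT but cannot be known before Day 37, while the DLT window, trigger, evaluability and MTD rule close at Day 21

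*Protocol*

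**What the plan says.** Protocol 5.2.3 opens its list of criteria with "The occurrence of any of the following toxicities during Treatment Cycle 1 will be considered a DLT", provided that the investigator judges the toxicity at least possibly related. One item on the list is "Prolonged delay (> 2 weeks) in initiating Cycle 2 due to treatment-related toxicity". Two other items depend on duration: grade 4 hematologic toxicity (thrombocytopenia apart) of at least 7 days, and a grade 3 or 4 non-hematologic laboratory value that continues for more than 1 week.

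The same section limits the observation window to the first 21-day cycle and says that AEs "meeting the definition of a DLT but occurring after this period will not be considered DLTs". Other rules use the same limit:

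- **De-escalation (3.1, repeated in 5.2.5.4):** the dose is reduced if at least 2 of the first 6, or at least 4 of 12, "Cohort 1 subjects experience a DLT in the first 21 days".
- **MTD (5.2.3):** it is "the highest dose level at which the subject incidence of a DLTs during the first 21-day cycle of investigational product dosing is < 33" per cent.
- **Evaluability (9.1):** a subject is evaluable after a DLT in the 21-day window or after completing the 21-day assessment.
- **Committee review (3.4):** "The data review will occur as soon as possible after Cycle 1 Day 21 of the last subject in Cohort 1".

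SAP 8.1.1 takes the DLT definition from Protocol 5.2.3 and adds no timing rule. SAP 11.1 plans a DLT table by preferred term. SAP 1 states that the study ended in Phase 1B with 12 subjects enrolled.

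**The concern.** The list contains a criterion that can only be observed after the count has closed. The text does not say whether a Cycle 1 toxicity that later delays Cycle 2 by more than 2 weeks is a DLT, and it does not hold such a subject open until the answer is known. A subject can therefore pass Day 21 as evaluable without a DLT, and a dose decision can be taken, before the criterion can be assessed.

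DLT incidence is a primary endpoint, and SAP 3.2 keeps it in the reduced report. The classification also decides treatment. Under 5.2.3 any DLT means withdrawal from both products, whereas a delay that is not a DLT leaves Cycle 2 open.

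**Working it through.** **Inputs.** Cycle length 21 days (Protocol 5.2); delay limit 2 weeks, 14 days (5.2.3); window 21 days (5.2.3); triggers of at least 2/6 and at least 4/12 (3.1, 3.5, 5.2.5.4); MTD limit below 33% (5.2.3); 12 subjects (SAP 1). Assumption: Cycle 2 Day 1 is due on Day 22. This follows from the cycle length; 5.2 gives visit windows for Days 8 and 15 but none for Day 1.

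**1. The plan's own limit.** 1/6 = 16.7% and 3/12 = 25.0% are below 33%. 2/6 = 33.3% and 4/12 = 33.3% are not. The MTD limit and the de-escalation counts agree.

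**2. When the delay criterion can be met.** Cycle 2 is due on Day 1 + 21 = Day 22. A delay of exactly 14 days is Day 22 + 14 = Day 36. A delay of more than 14 days is first reached on Day 37, which is 37 - 21 = 16 days after the window closes.

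**3. The duration criteria.** Count the onset day as the first day and call it d.

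- At least 7 days is reached on Day d + 6, which is later than Day 21 when d is 16 or more. Onset on Day 21 gives Day 27.
- More than 7 days is reached on Day d + 7, which is later than Day 21 when d is 15 or more. Onset on Day 21 gives Day 28.

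The gap is the same in kind, but shorter and limited to late onset.

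**4. The two readings.**

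| Dated by | Effect on the delay criterion | Consequence |
|---|---|---|
| The delay itself | Day 37 is always after Day 21, so it never counts | The criterion has no effect |
| Onset of the toxicity | A Cycle 1 toxicity can count | Status is unknown until Day 37, but 9.1 is satisfied at Day 21 |

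**5. Who is exposed.** Only subjects with no other DLT criterion by Day 21. Most nonhematologic events of grade 3 or higher qualify already, as does treatment-related discontinuation in Cycle 1. Missing one of the three Cycle 1 tabelecleucel doses through a related AE is 1/3 = 33%, above the 25% limit, so most events that disrupt Day 8 or Day 15 are also caught. What remains is mainly lower-grade related toxicity after the Day 15 dose. One possible example is grade 2 pneumonitis. Table 5 calls for pembrolizumab to be withheld and for 1-2 mg/kg prednisone, and 5.3.1.1 holds tabelecleucel while more than 0.5 mg/kg is needed. Both products could then be on hold at Day 22. Footnote a of Table 5 tempers this: "Withhold or permanently discontinue pembrolizumab is at the discretion of the investigator or treating physician".

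**6. Effect of one case.** 1/6 becomes 2/6 (16.7% to 33.3%), or 3/12 becomes 4/12 (25.0% to 33.3%). Either step crosses the de-escalation count and the 33% limit. From any other starting count among 12, one case adds 1/12 = 8.3 points to the incidence.

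**7. Chance of at least one case (illustration).** The documents give no rate. With an assumed rate q per subject, the chance in 12 subjects is 1 - (1 - q)^12: 22% at q = 2%, 46% at 5% and 72% at 10%.

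**The case against.** The strongest reply is that the text has one workable reading. The lead-in requires a toxicity during Cycle 1, and the exclusion is of AEs that occur later. A dosing delay is not an AE but a consequence that qualifies an earlier one, just as duration does for the hematologic and laboratory items. Dating all three by onset makes the list coherent; the other reading leaves the delay item idle. This largely stands, and the fix adopts it. It does not close the gap, because under the onset reading 9.1 still accepts the subject at Day 21 and nothing holds the decision.

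A second reply is that oversight does not stop at Day 21. Section 3.3 provides for review whenever a DLT is reported. Under 3.4 the medical monitor and global safety officer "may suspend dosing and/or enrollment and convene a SDRC meeting at any time based on emerging safety data". Section 3.5 states the de-escalation counts with no 21-day wording, and the scheduled review has an earliest date but no data cut-off. SAP 11.1 also tabulates TEAEs that lead to treatment interruption. All of this stands and reduces the harm. It makes a late case visible without saying whether it is counted.

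A third reply is that little remains to decide. Phase 2 was not run, SAP 2.2 describes the committee review as having taken place, and SAP sections 8 and 11 describe no MTD analysis. That also stands. For this study, the point now concerns only the reported DLT count.

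**Conclusion.** The point holds as a conflict between stated rules. Dated by its own occurrence, the delay criterion can never be met. Dated by onset, it can be met, but up to 16 days after the subject has been accepted as DLT-free. The size is one subject at a time: enough to reverse a decision at 1/6 or 3/12, and 8.3 points of incidence among 12. The result rests on Cycle 2 being due on Day 22 and on the case meeting no other criterion. It should be corrected, but it does not undermine the study.

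Three stronger conclusions might be inferred, and the documents do not support them:

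- **That a DLT was missed in Cohort 1.** The documents give neither the DLT count nor any Cycle 2 start date. The effect may be nil.
- **That every safety rule is locked to Day 21.** Sections 3.3, 3.4 and 3.5 show otherwise.
- **That the MTD or a Phase 2 dose is wrong.** A reversal needs exactly 1/6 or 3/12 DLTs plus a case of this kind, and neither is shown. No Phase 2 dosing took place.

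**What to change.** **Protocol, for any further use.** In 5.2.3, state that a related toxicity with onset on Days 1-21 is a DLT if it later meets the delay criterion or a duration criterion. In 9.1 and 3.4/3.5, keep such a subject pending until Cycle 2 starts, Day 36 has passed or the duration criterion is resolved. The cost is some wording and a wait of up to about 16 days (Day 21 to Day 37), for affected subjects only.

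**SAP, for the 12 subjects.** Put the same onset rule in 8.1.1. In the 11.1 DLT table, enter the case under the AE that caused it, since a delay has no preferred term of its own. Say whether one product given alone under Protocol 5.2.5.5 counts as starting Cycle 2, so that the start date is defined. Then check the 12 Cycle 2 start dates and any late-onset events under the duration criteria. If the count matches the DLTs called during the study, nothing more is needed. If it differs, report both counts, labelled, and leave the calls made during the study in place. The cost is a few sentences and a short data check.

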5.2.4 Discontinuation of Treatment with Investigational Products after Complete Response

Discontinuation of treatment may be considered for subjects who have attained a confirmed CR that have been treated for at least 6 weeks with tabelecleucel and 24 weeks with pembrolizumab and had at least 2 treatments with pembrolizumab and 1 cycle tabelecleucel beyond the date when the initial CR was observed.

While subjects achieving a CR may discontinue treatment, they will not be considered to have discontinued the study unless consent is withdrawn. If study consent is not withdrawn the subject will complete an End-of-Treatment visit and enter in the Quarterly Follow-up Phase of the study.

5.2.5 Dose Modifications

5.2.5.1 Dose Modification and Toxicity Management for Immune-related AEs associated with Pembrolizumab

AEs associated with pembrolizumab exposure may represent an immunologic etiology. These immune-related AEs (irAEs) may occur shortly after the first dose or several months after the

last dose of pembrolizumab treatment and may affect more than one body system simultaneously. Therefore, early recognition and initiation of treatment is critical to reduce complications. Based on existing clinical study data, most irAEs were reversible and could be managed with interruptions of pembrolizumab, administration of corticosteroids and/or other supportive care. For suspected irAEs, ensure adequate evaluation to confirm etiology or exclude other causes. Additional procedures or tests such as bronchoscopy, endoscopy, skin biopsy may be included as part of the evaluation. Based on the severity of irAEs, withhold or permanently discontinue pembrolizumab and administer corticosteroids. Dose modification and toxicity management guidelines for irAEs associated with pembrolizumab are provided in [Table 5](#), and refer to the approved label. See Section [5.3.1.1](#) for supportive care guidelines, including use of corticosteroids.

Table 5 Dose Modification and Toxicity Management Guidelines for Immune-related Adverse Events Associated with Pembrolizumab

General instructions:				
irAEs	Toxicity grade or conditions	Action taken to pembrolizumab ^a	irAE management with corticosteroid and/or other therapies	Monitor and follow-up
Pneumonitis	Grade 2	Withhold	Administer corticosteroids (initial dose of 1-2 mg/kg prednisone or equivalent) followed by taper	Monitor subjects for signs and symptoms of pneumonitis Evaluate subjects with suspected pneumonitis with radiographic imaging and initiate corticosteroid treatment Add prophylactic antibiotics for opportunistic infections
	Grade 3 or 4, or recurrent Grade 2	Permanently discontinue		
Diarrhea / Colitis	Grade 2 or 3	Withhold		

irAEs	Toxicity grade or conditions	Action taken to pembrolizumab ^a	irAE management with corticosteroid and/or other therapies	Monitor and follow-up
	Grade 4	Permanently discontinue	Administer corticosteroids (initial dose of 1-2 mg/kg prednisone or equivalent) followed by taper	Monitor subjects for signs and symptoms of enterocolitis (ie, diarrhea, abdominal pain, blood or mucus in stool with or without fever) and of bowel perforation (ie, peritoneal signs and ileus). Subjects with Grade \geq 2 diarrhea suspecting colitis should consider GI consultation and performing endoscopy to rule out colitis. Subjects with diarrhea/colitis should be advised to drink liberal quantities of clear fluids. If sufficient oral fluid intake is not feasible, fluid and electrolytes should be substituted via IV infusion.
AST / ALT elevation or Increased TBILI	Grade 2	Withhold	Administer corticosteroids (initial dose of 0.5-1 mg/kg prednisone or equivalent) followed by taper	Monitor with liver function tests (consider weekly or more frequently until liver enzyme value returned to baseline or is stable)
	Grade 3 or 4	Permanently discontinue	Administer corticosteroids (initial dose of 1-2 mg/kg prednisone or equivalent) followed by taper	
Type 1 diabetes mellitus (T1DM) or Hyperglycemia	Newly onset T1DM or Grade 3 or 4 hyperglycemia associated with evidence of β -cell failure	Withhold	Initiate insulin replacement therapy for subjects with T1DM Administer anti-hyperglycemic in subjects with hyperglycemia	Monitor subjects for hyperglycemia or other signs and symptoms of diabetes.
Hypophysitis	Grade 2	Withhold		

irAEs	Toxicity grade or conditions	Action taken to pembrolizumab ^a	irAE management with corticosteroid and/or other therapies	Monitor and follow-up
	Grade 3 or 4	Withhold or permanently discontinue	Administer corticosteroids and initiate hormonal replacements as clinically indicated.	Monitor for signs and symptoms of hypophysitis (including hypopituitarism and adrenal insufficiency)
Hyperthyroidism	Grade 2	Continue	Treat with non-selective beta-blockers (eg, propranolol) or thionamides as appropriate	Monitor for signs and symptoms of thyroid disorders.
	Grade 3 or 4	Withhold or permanently discontinue		
Hypothyroidism	Grade 2-4	Continue	Initiate thyroid replacement hormones (eg, levothyroxine or liothyroinine) per standard of care	Monitor for signs and symptoms of thyroid disorders.
Nephritis and Renal dysfunction	Grade 2	Withhold	Administer corticosteroids (prednisone 1-2 mg/kg or equivalent) followed by taper.	Monitor changes of renal function
	Grade 3 or 4	Permanently discontinue		
Myocarditis	Grade 1 or 2	Withhold	Based on severity of AE administer corticosteroids	Ensure adequate evaluation to confirm etiology and/or exclude other causes
	Grade 3 or 4	Permanently discontinue		
All other irAEs	Intolerable/ persistent Grade 2	Withhold	Based on type and severity of AE administer corticosteroids	Ensure adequate evaluation to confirm etiology and/or exclude other causes
	Grade 3	Withhold or discontinue based on the type of event. Events that require discontinuation include and not limited to: Guillain-Barre Syndrome, encephalitis		
	Grade 4 or recurrent Grade 3	Permanently discontinue		

irAEs	Toxicity grade or conditions	Action taken to pembrolizumab ^a	irAE management with corticosteroid and/or other therapies	Monitor and follow-up
Abbreviations: AE: adverse event; ALT: alanine aminotransferase; AST: aspartate aminotransferase; irAE: immune-related AE; IV: intravenous(ly); T1DM: type 1 diabetes mellitus; TBIL: total bilirubin.				
NOTE: For subjects with Grade 3 or Grade 4 immune-related endocrinopathy where withhold of pembrolizumab is required, pembrolizumab may be resumed when AE resolves to grade ≤ 2 and is controlled with hormonal replacement therapy or achieved metabolic control (in case of T1DM).				
^a Withhold or permanently discontinue pembrolizumab is at the discretion of the investigator or treating physician.				

5.2.5.2 *Dose modification and Toxicity Management of Infusion Reactions Related to Pembrolizumab*

Pembrolizumab may cause severe or life-threatening infusion reactions including severe hypersensitivity or anaphylaxis. Signs and symptoms usually develop during or shortly after drug infusion and generally resolve completely within 24 hours of completion of infusion. Dose modification and toxicity management guidelines on pembrolizumab associated infusion reactions are provided in [Table 6](#).

Table 6 Pembrolizumab Infusion Reactions Dose modification and Treatment Guidelines

CTCAE Grade	Treatment	Premedication at Subsequent Dosing
Grade 1 Mild reaction; infusion interruption not indicated; intervention not indicated	Increase monitoring of vital signs as medically indicated until the subject is deemed medically stable in the opinion of the investigator.	None
Grade 2 Requires therapy or infusion interruption but responds promptly to symptomatic treatment (eg, antihistamines, NSAIDs, narcotics, IV fluids); prophylactic medications indicated for ≤ 24 hrs.	Stop Infusion. Additional appropriate medical therapy may include but is not limited to: IV fluids Antihistamines NSAIDs Acetaminophen Narcotics Increase monitoring of vital signs as medically indicated until the subject is deemed medically stable in the opinion of the investigator.	Subject may be premedicated 1.5 hours (± 30 minutes) prior to infusion of pembrolizumab with: Diphenhydramine 50 mg PO (or equivalent dose of antihistamine). Acetaminophen 500 to 1000 mg PO (or equivalent dose of analgesic).

Table 6 Pembrolizumab Infusion Reactions Dose modification and Treatment Guidelines

CTCAE Grade	Treatment	Premedication at Subsequent Dosing
	
If symptoms resolve within 1 hour of stopping drug infusion, the infusion may be restarted at 50% of the original infusion rate (eg, from 100 mL/hour to 50 mL/hour). Otherwise dosing will be held until symptoms resolve and the subject should be premedicated for the next scheduled dose.
 
Subjects who develop Grade 2 toxicity despite adequate premedication should be permanently discontinued from further study drug treatment
	
Grade 3 or Grade 4 Grade 3: Prolonged (ie, not rapidly responsive to symptomatic medication and/or brief interruption of infusion); recurrence of symptoms following initial improvement; hospitalization indicated for other clinical sequelae (eg, renal impairment, pulmonary infiltrates) Grade 4: Life-threatening; pressor or ventilator support indicated	
Stop Infusion.
 
Additional appropriate medical therapy may include but is not limited to:
 
Epinephrine** IV fluids Antihistamines NSAIDs Acetaminophen Narcotics Oxygen Pressors Corticosteroids
 
Increase monitoring of vital signs as medically indicated until the subject is deemed medically stable in the opinion of the investigator.
 
Hospitalization may be indicated.
 
**In cases of anaphylaxis, epinephrine should be used immediately.
 
Subject is permanently discontinued from further study drug treatment.
	No subsequent dosing

Abbreviations: IV: intravenous(ly), NSAID: nonsteroidal anti-inflammatory drug, PO: per os/by mouth.
Appropriate resuscitation equipment should be available at the bedside and a physician readily available during the period of drug administration. For further information, please refer to CTCAE version 5.

